Study Protocol

An Insight on the Relationship Between the Variation in Medication Adherence Level and the Clinical Outcomes among Tuberculosis and Human Immunodeficiency Virus Co-Infected Patients

1. Background and Significance

Tuberculosis (TB) is a leading cause of death in young people and adults (1). The control of tuberculosis remains a major public health challenge in all parts of the world. In some geographical areas, particularly in low and middle-income countries, TB incidence is increasing rapidly and is often associated with a high prevalence of human immunodeficiency virus (HIV) (2). DOTS (directly observed treatment, short course) is the internationally recommended control strategy for TB. This strategy includes the delivery of a standard short course of drugs, lasting 6 months for new patients and 8 months for retreatment patients diagnosed with TB. The delivery includes the direct observation of therapy (DOT), either by a health worker or by someone nominated by the health worker and the patient for this purpose (sometimes called a DOT supporter). The strategy has been promoted widely and implemented globally (3). A qualitative approach and pharmacist-led intervention are needed to improve the adherence level of medication for TB patients.

2. Literature review

In 2019, out of 10 million people who had TB, 8.2% were diagnosed with HIV (4). According to the Ministry of Health, 87,581 persons were living with HIV in Malaysia as of 2019. Only 77,903 people are aware of their situation. According to the United Nations, Malaysia is one of the 10 nations responsible for over 95% of all new HIV infections in the Asia-Pacific area in 2016. TB is a disease with high prevalence and high mortality in many developing nations. Antiretroviral therapy (ART) has improved in effectiveness over the last few decades, allowing PLWH to live longer. Though antiretroviral medication adherence remains a significant predictor of treatment success, there is currently no gold standard tool for reliably measuring ART adherence, and scientists and researchers are still working on new methods to achieve this aim. Current anti-TB therapy (ATT) consists of a cocktail of drugs taken over at least 6-8 months. Because of the long duration of the therapy, there is a risk of treatment interruption or default, a phenomenon that contributes to prolonged infectiousness, relapse, and drug resistance.

The difficulty experienced by patients in following treatment regimens has raised the awareness of adherence as a complex behavioral issue. Efforts to improve treatment outcomes require a better understanding of particular barriers to and facilitators of patient adherence. Although the available anti-TB drugs are effective and supplied free of charge in many national TB programs (NTPs), non-adherence to ATT is a major barrier to global control. It may result in persistent infectiousness and higher rates of treatment failure, relapse, and drug resistance, requiring more prolonged and expensive treatment that is less likely to be successful than treatment for drug-susceptible TB.

The prolonged treatment period can have detrimental effects on the patient's health-related quality of life (HRQoL). Reduced HRQoL has been attributed to symptoms of TB, side effects of drug therapy, societal stigma, economic costs, anxiety, and depression during the treatment process. Adherence is measured by outcome-oriented (e.g. cure rate) and process-oriented (e.g. visit attendance, pill counts) methods (5). It can also be measured by direct and indirect methods. The direct method involves directly observed therapy (DOT), detection of drugs and metabolites in urine and blood, and involves ingestible sensor-based system. DOT is founded on the idea that a trained and monitored agent – such as a health worker, a community volunteer, or a family member

– directly supervises patients ingesting their anti-TB drugs.

Anti-TB medications or their metabolites can be measured to provide objective proof of drug intake by the patient. This, together with its ability to be conducted at the point-of-care level, should be considered the key advantage of the Direct method of adherence measurement.

Yellow	Negative	Urine color remains unchanged.
Purple Blue	Positive	INH was taken recently.
Green	Equivocal	Drugs have been taken recently but not within the last 30 hours

3. Research aim and objectives

The study is aimed to investigate the degree of adherence and evaluate its impacts on clinical outcomes in TB and HIV co-infected patients.

3.1 Specific Objectives

1. To perform a systematic review and meta-analysis on evidence-based TB drug adherence.

2. To determine the association between the pharmacist-led intervention and medication adherence level among TB and HIV co-infected patients.
3. To assess the effects of different levels of adherence with therapeutic impact and its possible clinical outcomes.
4. To assess the survival trend with the study population and health-related quality of life (HRQoL) by using the EQ5Dv3 tool.
5. To assess the defaulter patients' approach towards TB and its treatment outcomes.
(Qualitative Approach)

4. Ethical Approval

The study protocols will be approved by the Ethical and Research Committee Ministry of Health, Malaysia. The protocol will also be registered at clinicaltrials.gov

5. Methodology

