5.4. Data Collection and Management

A trained healthcare professional team will collect and supervise the data collection. Enrolled participants will answer a brief questionnaire focused on recent isoniazid adherence. Patients will be asked to report their recent adherence, including the date of their most recent dose. They will be also asked to estimate how many of the last thirty doses they had missed or how many doses they missed in a typical week and the reasons for any missed doses. Data will be collected from the primary source through interviews and sample urine collection, and a secondary source by a review of the health facility attendance registration book to confirm the patient's medication refill visit attendance. A trained pharmacist and nurses will collect urine specimens in a clean and dry container. Urine collected at any time of the day may be used. The sample does not have to be freshly voided as the sample can be stored at room temperature for 1 to 10 days and thereafter at -20°C and retain its suitability for testing. The urine sample will be collected on day 0, and then after every 2 months i.e., 2 months, 4 months, and 6 months. The urine sample will be discarded immediately after the analysis. A health worker will be trained to administer the EQ-5D. Enrolled patients will be explained the purpose and duration of the study. All participants included in the study provided informed consent and completed the EQ-5D facilitated by the trained health worker in a face-to-face interview at the clinic. The interview will be conducted on the premises of the hospital. Interviews will be conducted at the start of the study, after 2 2-month visits, and then at the end of the study (6th month). To ensure the security of the patients' information, a double-blind randomization technique will be adopted. The computer gives each patient a code number, and the code numbers will then be allocated randomly to the treatment groups. All data will be kept in a database, and backup file with password protectors. All identifiable information will be removed

And replaced by code. Code breaking will be done by the external personnel who are not involved in the study so the biasedness couldn't be possible. At the end of the trial, the patients can check their records on request. The study record shall be destroyed after the research is completed.

5.5. Study End Point:

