The study will be ended after 6th month, but still, if the patients are non-adherent to the therapy the study period will be extended to 1 year.

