5.10 Rationale for collection of specimens

Treatment adherence for coinfection diseases is difficult due to the complexity, low tolerability, and extended duration of current treatment regimens, especially for both drug-susceptible and drug-resistant TB. As a result, poor adherence raises the chance of treatment failure, relapse, and the development or amplification of drug resistance. Studies have shown rates of non-adherence to be typically 8–33% [5]. The adherence metrics used in research studies and clinical practice have a big impact on the clinical outcomes of the disease. However, near-perfect adherence is required to increase the chances of long-term clinical success. More research is needed on the factors that influence treatment adherence in TB and HIV patients receiving concurrent treatment. As a result, we will undertake a study to learn more about evidence-based adherence and treatment outcomes in TB and HIV patients.

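### No TB or HIV clinical outcome is defined, scheduled or analysed, so the stated aim and objective 3 cannot be answered as written

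*Combined protocol and SAP*

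**What the plan says.** The title announces the "Relationship Between the Variation in Medication Adherence Level and the Clinical Outcomes". The aim in section 3 is to "investigate the degree of adherence and evaluate its impacts on clinical outcomes in TB and HIV co-infected patients". Objective 3 in section 3.1 reads "To assess the effects of different levels of adherence with therapeutic impact and its possible clinical outcomes". None of the three names an outcome. The nearest neighbour is objective 4: "To assess the survival trend with the study population and health-related quality of life (HRQoL) by using the EQ5Dv3 tool". Objective 5 mentions treatment outcomes among defaulters, as a qualitative question.

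On data, section 5.4 says "Data will be collected from the primary source through interviews and sample urine collection", with a secondary source described as a "review of the health facility attendance registration book to confirm the patient's medication refill visit attendance". The same section adds EQ-5D interviews. Urine is collected on day 0 and at months 2, 4 and 6.

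Section 5.2 lists smear, culture, Xpert Ultra and chest X-ray for people with HIV who have TB symptoms, without timing. It describes a 2-month intensive phase followed by a 4-month continuation phase.

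Section 5.5 states "The study will be ended after 6th month", with an extension to 1 year if patients are non-adherent. Section 5.8 describes comparisons between the arms and an ANOVA on the monthly accumulated adherence rate. Section 10 restricts the analysis to patients who stay to the end. Section 5.10 gives as motivation that "poor adherence raises the chance of treatment failure, relapse, and the development or amplification of drug resistance".

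**The concern.** The study's headline question relates adherence (the exposure) to clinical outcomes (the response). The plan measures the exposure three ways and never specifies the response. If the study is run exactly as written, it ends with adherence data and EQ-5D, and no TB or HIV outcome to set against adherence. Analysis cannot recover outcomes that were never recorded, so this has to be settled before data collection.

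A second problem is that the length of observation depends on the exposure. Only non-adherent patients are followed beyond month 6, so any later event would be seen mainly in that group. Comparing such events between adherence groups would be biased by design.

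**Working it through.** The plan gives no figure to reproduce here. The check sets the promise against collection, analysis and follow-up.

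**1. What is collected (section 5.4).**

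| Item | What it measures | TB or HIV clinical outcome? |
|---|---|---|
| Adherence questionnaire | Exposure, self-reported | No |
| Urine isoniazid test | Exposure, recent intake | No |
| Attendance register | Exposure, refill visits | No |
| EQ-5D | Quality of life, objective 4 | No |

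That is 0 of 4. Follow-up bacteriology, cure, failure, death, viral load and CD4 do not appear. Objectives 4 and 5 mention survival and treatment outcomes, but 5.4 describes collecting neither.

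**2. What might fill the gap.** The tests in 5.2 appear once, in the paragraph on enrolment, and only for patients with symptoms. Even if used later, they would not give an outcome for every patient. Section 12 anticipates approval for access to clinical information but names no variable or time point.

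**3. What is analysed (section 5.8).** The t-test, chi-square, Fisher and logistic methods are tied to differences between arms. The ANOVA is tied to adherence rate by arm. A random-effects structure is mentioned without naming its response. No analysis has adherence level as the explanatory variable and a clinical outcome as the response.

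**4. Who is analysed (section 10).** Withdrawn patients are excluded. If deaths and losses are handled as withdrawals, those outcomes would drop out even if noted.

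**5. Time observed off treatment.** Inputs: course length 2 + 4 = 6 months (5.2); follow-up 6 months, or 12 if extended (5.5); time on treatment at enrolment 0 to about 1 month (5.6 requires diagnosis within the past month; I assume treatment begins at diagnosis).

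Off-treatment time = follow-up + time already on treatment − 6.

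- Stops at month 6: 6 + 0 − 6 = 0 months, or 6 + 1 − 6 = 1 month.
- Extended to 1 year: 12 + 0 − 6 = 6 months, or 12 + 1 − 6 = 7 months. This assumes the patient finishes a 6-month course on time. The documents do not say so, and it is doubtful for patients extended because of non-adherence.

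**6. Calendar.** Section 5.2 gives November 2022 to November 2023, 12 months. Full 6-month follow-up needs enrolment in the first 12 − 6 = 6 months. A full 1-year extension needs enrolment at month 12 − 12 = 0, so it fits only patients enrolled at the very start. The 6 to 7 months in step 5 is therefore a ceiling that few could reach. No visits or measurements are scheduled in the extension.

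**The case against.** The strongest reply is that end-of-treatment outcomes fall at or near month 6, so the existing follow-up could capture cure, failure or death. That is correct, and it limits the point: what is missing is definition, collection and analysis. Longer follow-up is not what objective 3 chiefly needs.

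A reader might infer that the study fails because it cannot see relapse. The documents do not support that. Relapse appears only as background (sections 1, 2 and 5.10) and objective 3 does not name it. It is essentially unobservable in patients who stop at month 6, but that alone does not defeat the objective. Nor does follow-up simply stop with the course, since 5.5 provides an extension. The requirement in 5.6 of no planned move within 9 months also looks beyond month 6, though no visit is attached to it.

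A reader might also infer that no patient outcome of any kind is collected. EQ-5D is collected and could be related to adherence. It belongs to objective 4 and is neither a TB nor an HIV clinical outcome.

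Finally, 5.2 does not rule out repeat bacteriology; the accurate statement is that none is scheduled. The comparison of arms on adherence under objective 2 does not need these data and is unaffected.

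**Conclusion.** The point holds in this form: no TB or HIV clinical outcome is defined, scheduled or analysed, so the aim and objective 3 cannot be answered from the plan as written. It must be fixed because the title and aim rest on it. This conclusion needs no numerical assumption.

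The secondary point also holds. Observation off treatment is about 0 to 1 month for patients who stop at month 6 and at most 6 to 7 months for extended non-adherent patients. Both ranges assume that treatment starts between diagnosis and enrolment and that the 6-month course is completed on time, and the second is further limited by the study window. The direction does not depend on those figures: extra observation is given to one exposure group only.

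**What to change.** 1. **Section 5.4.** For every randomised patient, abstract from the treating facility's TB records the end-of-treatment outcome (cured, completed, failed, died, lost), with its date. Add any routine viral load or CD4 on file nearest the start and end of treatment.
2. **Section 3.1.** Restate objective 3 in terms of end-of-treatment outcome, and say that no conclusion on relapse will be drawn. State that events seen only in the extension will not be compared between adherence groups.
3. **Section 5.8.** Add a regression of the end-of-treatment outcome on adherence recorded before the outcome date. The date matters: a patient enrolled one month into treatment finishes at study month 6 − 1 = 5, so the month-6 urine result comes after the outcome. Report loss or default separately, because refill attendance is itself an adherence measure and the association would be partly circular.
4. **Section 10.** Keep withdrawn, deceased and lost patients in this analysis where consent allows, instead of completers only.

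The cost is one abstraction form, and section 12 already foresees approval for access to clinical information. The workload depends on how many places hold the records: 5.3 and 5.6 refer to facilities and sites in the plural, and that a TB record with these categories exists at each is an assumption to confirm. Objective 3 becomes narrower and the HIV laboratory values will be incomplete. Section 6 gives no event rate for a clinical outcome (its 5.9% is a co-infection prevalence), so the association should be reported as an estimate with a confidence interval.

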5.1 Study Design

A longitudinal study design will be adopted to achieve the present study objectives. The study population will be classified with one intervention and one control arm, using a 1:1 allocation ratio, to evaluate whether the intervention is superior to the control treatment will be adopted to achieve the study objectives at General Hospital Penang.

Intervention arm: Enrolled participants will be counseled and educated by a pharmacist on the therapy and benefits of adherence.

Control arm: Enrolled patient will be counseled and educated by the material provided on the therapy and benefits of adherence.

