5.2 Study Setting

The study will be conducted at Hospital Pulau, Penang from November 2022 to November 2023. We will enroll patients with culture-confirmed TB. Additionally, the enrolled PLHIV with any TB symptoms will be investigated with sputum smear microscopy, mycobacterial culture (BACTEC MGIT), Xpert Ultra, and Chest X-ray (CXR). Patients will be eligible for enrolment if they are ≥ 18 years of age, diagnosed with active TB according to national TB program guidelines, had not been previously treated for these diseases, agreed to start treatment for TB, and could give informed consent in either English or Malay.

In Malaysia, a DOT program has been implemented in two phases, “intensive” and “continuation”. In the intensive phase (daily DOT) the current standard anti-TB regimen recommended by WHO

Consists of a 2-month treatment with INH, rifampicin (RIF), pyrazinamide (PZA), and ethambutol(EMB), followed by a 4-month continuation phase with INH and RIF (2EHRZ/4HR) as daily regimen. In the intensive phase (daily DOT), a patient takes their medication in front of the healthcare worker every day at a health facility. In the continuation phase (non-daily DOT), a patient is given the responsibility to take the medication at home and come to a health facility weekly for health checking and medication refilling.

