Subjects can choose to withdraw at any time. Subjects may be withdrawn if the investigator deems that it is detrimental or risky for the subject to continue. As this is a prospective observational study and data in the form of information are only required, the literature suggests about 10-20% dropout or withdrawal has been observed in the past so 20% dropout is already included in the sample size calculation thus the withdrawn subjects will not be replaced with new subjects.

10. Selection of subjects to be included in the analysis

All the subjects who will participate until the end of this study will be included in the final analysis of this study. All subjects who withdraw from the study at any point in time will not be included in the final results analysis.

11. Risk-Benefit Assessment

As stated above, there is no risk from the investigational process and study procedures. No harm could be caused to the patient as there is no invasive procedure involved in the study nor any

Medication is given to the patient. Only non-clinical intervention is given in the study. Study findings shall potentially improve treatment outcomes. The expected benefit outweighs the minimal risk to subjects and thus this study should be supported.

If still any injuries do occur as a direct result of participating in the study, treatment for such injuries shall be provided or paid for by the researcher/ sponsor.

12. Ethics of Study

The study will be conducted in compliance with ethical principles outlined in the Declaration of Helsinki and the Malaysian Good Clinical Practice Guideline.

All aspects of the study protocol, including access to and the use of clinical information of patients, and demographics will get approval by the institutional medical ethics committee locally as well as central health authorities before initiation of this study. Information on individuals will be strictly protected and used for clinical research only.

13. Informed Consent/Assent Process

Patients shall be informed of the study during their usual clinic visits. They will be requested to contact investigators if they are interested. An appointment will be made where the patient information sheet will be provided and explained to them. If they are willing to participate, the consent forms will be signed and dated. If they need to, they are allowed to take the information sheet home to consult with their family members, and another day for getting consent arranged.

14. Conflict of Interest

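### Objective 3 asks for the effect of adherence on clinical outcomes, but adherence is not randomised, HIV-severity markers are not listed as data, and no adjusted adherence-outcome model is given

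*Combined protocol and SAP*

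**What the plan says.** **Question.** Section 3 says the study will "evaluate its impacts on clinical outcomes in TB and HIV co-infected patients". Objective 3 in section 3.1 is "To assess the effects of different levels of adherence with therapeutic impact and its possible clinical outcomes".

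**What is allocated.** Section 5.1 assigns pharmacist counselling or printed material "using a 1:1 allocation ratio". Adherence level is not assigned.

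**Data.** Section 5.4 says "Data will be collected from the primary source through interviews and sample urine collection", with refill attendance taken from the facility register. Urine is tested at day 0 and months 2, 4 and 6. For EQ-5D: "Interviews will be conducted at the start of the study, after 2 2-month visits, and then at the end of the study (6th month". Under section 5.2, enrolled patients with HIV and TB symptoms are "investigated with sputum smear microscopy, mycobacterial culture (BACTEC MGIT), Xpert Ultra, and Chest X-ray (CXR". CD4 count, viral load, ART status and TB site are not listed as data items anywhere.

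**Analysis.** Section 5.8 assigns the t-test, chi-square, Fisher's exact test and logistic regression to the comparison of the two arms. The ANOVA of accumulated adherence also compares the arms. A model with random intercept and slope is mentioned without an outcome, exposure or covariates.

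**Follow-up and analysis set.** Section 5.5 ends the study at month 6 but extends it to one year for non-adherent patients. Section 10 leaves out everyone who withdraws.

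**The concern.** Randomisation protects the comparison of arms. It does not protect the comparison of adherent with non-adherent patients, because adherence arises after allocation and depends on the patient's condition. If advanced disease both lowers adherence and worsens outcome, non-adherent patients will do worse even when missed doses have no effect.

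Every participant is meant to be HIV co-infected (section 5.3), and section 2 itself ties virologic and immunologic results to ART adherence. Immune and ART status are thus obvious candidate confounders. If they are not recorded, no later analysis can adjust for them. At stake is the study's stated aim: the report could present as an effect of adherence something that is partly or wholly a difference in severity.

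**Working it through.** **1. The plan's own figure.** There is none for this objective. The 382 in section 6 is for the arm comparison; I use it as stated, only to gauge false-positive rates.

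**2. Plan against question.** Sections 3 and 3.1 ask what adherence does to outcomes. Section 5.8 describes arm comparisons and one unspecified mixed model. No sentence links adherence to an outcome, names a covariate, or orders adherence before outcome in time.

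**3. Size under moderate-to-strong confounding.** All inputs are assumptions, and the true adherence effect is set to zero:
- share with advanced HIV, h = 30–50%;
- non-adherence a0 = 15% without and a1 = 30–45% with advanced HIV;
- poor outcome r0 = 5% without and r1 = 15–25% with it.

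Overall non-adherence is p = h·a1 + (1−h)·a0. The share with advanced HIV is sN = h·a1/p among the non-adherent and sA = h(1−a1)/(1−p) among the adherent. The crude risk ratio is [sN·r1 + (1−sN)·r0] / [sA·r1 + (1−sA)·r0].

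- Low end (h = 0.50, a1 = 0.30, r1 = 0.15): p = 0.225; sN = 0.150/0.225 = 0.667; sA = 0.350/0.775 = 0.452. Risks are 0.1167 and 0.0952; ratio **1.23**.
- High end (h = 0.30, a1 = 0.45, r1 = 0.25): p = 0.240; sN = 0.135/0.240 = 0.5625; sA = 0.165/0.760 = 0.217. Risks are 0.1625 and 0.0934; ratio **1.74**.

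Overall non-adherence across the grid is 19.5–30%, inside the 8–33% quoted in section 5.10. The grid implies severity odds ratios of (0.30/0.70)/(0.15/0.85) = 2.4 to (0.45/0.55)/(0.15/0.85) = 4.6 for non-adherence. For poor outcome they are (0.15/0.85)/(0.05/0.95) = 3.4 to (0.25/0.75)/(0.05/0.95) = 6.3. These are not weak associations.

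**4. Size when confounding is weaker.** Assume 40% severe, 10% poor outcome if not severe, and one severity odds ratio k for both non-adherence and poor outcome, again with zero true effect. Overall non-adherence is varied over 8–33%. The last column is the chance of p < 0.05 in the harmful direction with 382 patients (normal approximation for two proportions; nominal 2.5%).

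| k | Spurious odds ratio | Chance of a false harmful finding |
|---|---|---|
| 1.5 | about 1.04 | about 3% |
| 2 | about 1.12 | 5–6% |
| 3 | 1.32–1.33 | 10–18% |
| 4 | 1.51–1.56 | 18–38% |

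Example, k = 2 with 20% overall non-adherence: non-adherence is 15.5% in non-severe and 26.8% in severe patients. The severe share is 53.6% of the non-adherent and 36.6% of the adherent. Risks are 14.4% and 13.0%; odds ratio 1.12.

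**5. Direction.** If sicker patients adhere better, the bias reverses. Take h = 0.50, non-adherence 15% with and 45% without advanced HIV, r1 = 0.25, r0 = 0.05. Then p = 0.30, sN = 0.075/0.30 = 0.25 and sA = 0.425/0.70 = 0.607. Risks are 0.100 and 0.171; ratio 0.58. A real harm of non-adherence could be masked.

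**6. Time at risk and selection.** Under section 5.5 non-adherent patients can be observed for 12 months and the others for 6, so outcomes counted to the end of each patient's follow-up favour more events in the non-adherent. Section 10 then removes withdrawals, which may relate to both adherence and outcome. The documents do not allow either to be sized.

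**The case against.** The strongest reply is that the plan is looser than it is wrong. The title speaks of a relationship, objective 2 speaks of association, and the causal words in the aim and objective 3 may be loose phrasing. That stands as a reason to treat this as an improvement and not a fatal flaw. It does not supply the missing model or data items.

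Four stronger readings are tempting, and the documents do not support them.

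- *No baseline severity data are collected.* EQ-5D is taken at the start, and smear, culture, Xpert Ultra and chest X-ray are done in symptomatic patients with HIV. These can carry severity information, although they do not measure immune or ART status. Section 12 also foresees "access to and the use of clinical information of patients, and demographics", so record data could be used.
- *Objective 3 will be analysed with unadjusted t-tests and chi-square tests.* Section 5.8 assigns those to the arm comparison. The analysis of objective 3 is absent; its form is not known.
- *Early death or stopping will be scored as low adherence.* A fully adherent patient whose treatment ends at month 3 would score 90/180 = 50% over a full course but 90/90 = 100% over doses due to date. The denominator is not stated, and the completers-only rule may drop that patient. The overlap of adherence and outcome in time is shown only for EQ-5D, because clinical outcomes are not defined or dated.
- *The bias must exaggerate harm.* It could run either way, and it is small if severity associations are weak.

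**Conclusion.** The point holds in this form: a causal question about a non-randomised exposure, key HIV-severity variables not listed for collection, and no prespecified adjusted analysis. Carried out as written, the plan leaves objective 3 open to confounding that could not later be adjusted for HIV severity.

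The size is conditional. The crude risk ratio of 1.23 to 1.74 rests wholly on the assumed inputs. At severity odds ratios of 2 or less the bias is minor; at 3 to 4 it is material. The documents give nothing that places this population on that range, which is itself a reason to collect the variables. The randomised comparison of arms is not affected by this point.

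**What to change.** **Section 5.4.** At day 0, abstract from the clinic record CD4 count, viral load, ART status and start date, TB site, and days on TB treatment. The last can vary at entry because section 5.6 admits patients up to a month after diagnosis.

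**Section 5.8, objective 3.** Define the outcome at a time point common to all patients, whatever their length of follow-up. Regress it on adherence, adjusted for arm, baseline EQ-5D and a small prespecified set of the abstracted variables. Compute adherence over doses due before the outcome, and state the denominator.

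Keep a landmark analysis (adherence to month 4, outcomes after it) as a sensitivity analysis only. With 8–15% poor outcomes overall, as the assumptions above imply, 382 patients give 31–57 events. If these were spread evenly over six months, one third, about 10–19, would fall after month 4. That is too few for about seven parameters (adherence, arm and five covariates).

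**Sections 3 and 3.1.** Replace *impacts* and *effects* with *association*, and keep causal claims for the randomised arm comparison.

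**Cost.** A short abstraction form (section 12 already seeks approval for use of clinical information), some missing record values, and a more modest conclusion for objective 3. Adjustment does not remove unmeasured confounding or the selection from the completers-only rule in section 10; the report should say so.
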